4.2. Study Objectives

4.2.1. Primary Clinical Objective

- To assess the antitumor activity of dostarlimab in patients with recurrent or advanced mismatch repair deficient (dMMR)/microsatellite instability-high (MSI-H) endometrial cancer, in terms of objective response rate (ORR) and duration of response (DOR) based on investigators' assessment using Response Evaluation Criteria in Solid Tumors (RECIST) v1.1.

4.2.2. Secondary Clinical Objectives

- To assess the effectiveness of dostarlimab in terms of investigator-assessed progression-free survival (PFS) and overall survival (OS).
- To analyze the PFS rate at 6, 12, 18 and 24 months.

- To assess the disease control rate (DCR) based on investigators' assessment using RECIST 1.1.
- To evaluate duration of treatment with dostarlimab.
- To describe the time to response to dostarlimab.
- To evaluate the safety and tolerability of dostarlimab in patients with dMMR/MSI-H endometrial advanced cancer, including immune-related adverse events of interest (irAEI).
- To evaluate Neutrophil-to-lymphocyte ratio as a potential predictive biomarker for treatment with dostarlimab.

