1.1.2. Secondary Clinical Objectives

- To assess the effectiveness of dostarlimab in terms of investigator-assessed progression-free survival (PFS) and overall survival (OS).
- To analyze the PFS rate at 6, 12, 18 and 24 months.
- To assess the disease control rate (DCR) based on investigators' assessment using RECIST 1.1.
- To evaluate duration of treatment with dostarlimab.
- To describe the time to response to dostarlimab.
- To evaluate the safety and tolerability of dostarlimab in patients with dMMR/MSI-H endometrial advanced cancer, including immune-related adverse events of interest (irAEI).
- To evaluate Neutrophil-to-lymphocyte ratio as a potential predictive biomarker for treatment with dostarlimab.

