In the last 5 years, immunotherapy is undergoing an important development in EC. The first evidence of clinical activity of an immunotherapy in EC was obtained in a phase II trial published in 2015. The efficacy of the anti-programmed cell death 1 (anti-PD-1) monoclonal antibody pembrolizumab was studied in three cohorts of patients with metastatic solid tumors: dMMR colorectal cancer, pMMR colorectal cancer, and dMMR non-colorectal cancer. The ORR and progression-free survival (PFS) at 20 weeks for the dMMR non-colorectal cancer cohort (which included 2 EC patients) was 71% and 67%, respectively (11). These results confirmed the role of MMR status as a predictive biomarker to immunotherapy, and pembrolizumab was the first treatment approved by United States Food and Drug Administration (FDA) for dMMR tumors that had progressed to a previous line of treatment, regardless of the type of neoplasm. Other anti-PD-1 and anti-PD-L1 antibodies, like avelumab

or durvalumab, have achieved ORR ranging from 27% to 58% in highly pretreated patients with dMMR EC (12,13).

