4. STUDY DESIGN

4.1. Overview

This is a multicenter, retrospective, observational (non-interventional) study, in patients treated in a real-world setting within the Spanish dostarlimab EAP. The study is planned to be conducted in the Medical Oncology departments at 50-60 Spanish GEICO-associated hospitals. Its multicenter nature aims to improve the representativeness of the study population in Spain. The study would include approximately 110 patients with dMMR/MSI-H recurrent or advanced EC, that have progressed on or following prior treatment with a platinum-containing regimen, treated within the dostarlimab EAP, available in Spain from January 2021 to September 2022. The total number of participating centers and patients will be confirmed once the EAP is closed.

Patient's medical records will be screened by local clinical staff to assess for eligibility according to selection criteria. The study comprises a single study visit, in which the patient will give her informed consent to participate (when the patient is alive) and the physician will extract the study data from the patient's medical charts.

Alive patients who fulfill inclusion criteria and meet no exclusion criteria will be informed by a member of their care team about the purpose of the study, as well as about potential risks and benefits of study participation. The written informed consent form (ICF) should be signed prior to study initiation in alive patients in order to access their medical records. Deceased patients will be still included but their relatives will not be contacted. In these instances, data will be collected by members of the direct care team, unless there is a prior express order from the patient to preserve confidentiality. All eligible deceased and consenting living patients at the participating centers will be included. Data will be directly retrieved from hospital medical records and reported in the electronic Case Report Form (eCRF).

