4.5. Participant Selection

- Patients must meet all the following EAP inclusion criteria and none of the exclusion criteria to be eligible.
- Participants must have received dostarlimab (at least 1 cycle) within the Spanish EAP.

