5.5. Baseline (pre-dostarlimab)

- ECOG
- Existence of measurable disease
- CA 125

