6. SAMPLE SIZE

The study will include between 100-110 patients in total (retrospective in all cases) recruited in 50-60 sites.

The population will include all patients who received dostarlimab at least during one cycle as part of the EAP in GEICO-associated hospitals. The sample size will be based on the number of patients treated in the EAP of Spain.

There will be no formal calculation of the sample size. Most patients included in the Spanish EAP will be analyzed.

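### The neutrophil-to-lymphocyte ratio is set up as a predictive biomarker in a cohort where everyone was treated, and the protocol's data list has no item from which to compute it

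*Protocol*

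**What the plan says.** The objective appears in the synopsis (Section 1.1.2, "To evaluate Neutrophil-to-lymphocyte ratio as a potential predictive biomarker") and again in Section 4.2.2 ("To evaluate Neutrophil-to-lymphocyte ratio as a potential predictive biomarker for treatment with dostarlimab").

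The population consists of treated patients only:

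- Section 4.1 describes a retrospective, observational study "in patients treated in a real-world setting within the Spanish dostarlimab EAP".
- Section 4.5 states "Participants must have received dostarlimab (at least 1 cycle) within the Spanish EAP".
- Section 6 takes in "all patients who received dostarlimab at least during one cycle as part of the EAP", with 100 to 110 patients expected.

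No untreated or differently treated group is mentioned anywhere.

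Section 5 lists the data to be collected. Baseline Section 5.5 has three entries: ECOG, "Existence of measurable disease" and CA 125. Section 8.2 adds that the individual eCRF fields are set out in a separate specification, which is not at hand. Section 8.4 discusses incomplete charts, missing data and under-recorded adverse events. It does not mention the lack of a comparator.

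**The concern.** A marker is predictive for a treatment when the effect of that treatment differs by marker level. A treatment effect is a contrast between treated and not treated, and here the second half of the contrast does not exist. The objective therefore names a property that the design cannot estimate.

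The label has consequences in this document. Section 2.3 speaks of "the role of MMR status as a predictive biomarker to immunotherapy" in the same sentence that reports a drug approval for dMMR tumors. A reader who meets the same term attached to NLR may take it as a statement about whom to treat. Followed as written, an association seen only in treated patients would be reported under that heading.

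The second problem is practical. If the eCRF follows Section 5, the objective has no input. If it does not, the protocol's own list fails to show what the objective rests on.

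**Working it through.** The protocol gives no figure for this objective, so there is none to reproduce. Two checks were made.

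**1. Can treated-only data separate predictive from prognostic?**

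An illustration with assumed response rates:

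- *Dostarlimab:* ORR 55.5% with low NLR and 35.5% with high NLR, in equal halves. The average is (55.5 + 35.5)/2 = 45.5%, the latest GARNET figure in Section 2.4.2. The 20-point split is assumed.
- *Hypothetical comparator:* average ORR 10.5%, the midpoint of the 7% to 14% given for second-line drugs in Section 2.2.

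Within the treated cohort, the odds ratio (low against high NLR) is

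(0.555/0.445) / (0.355/0.645) = 1.247/0.550 = 2.27.

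Three comparators are all compatible with exactly these treated data:

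| Comparator ORR, low / high NLR | Comparator odds ratio | Interaction odds ratio | Drug effect in points, low / high NLR |
|---|---|---|---|
| 14.2% / 6.8% | 2.27 | 2.27/2.27 = 1.00 | 41.3 / 28.7 |
| 10.5% / 10.5% | 1.00 | 2.27/1.00 = 2.27 | 45.0 / 25.0 |
| 20.5% / 0.5% | not needed | not needed | 35.0 / 35.0 |

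In the first row NLR is purely prognostic on the odds-ratio scale. In the second it is predictive. In the third, an extreme case, there is no interaction on the difference scale. The treated cohort looks the same in all three, so it cannot tell them apart on either scale. The number of comparator patients is 0 of the planned 100 to 110, and increasing the cohort leaves it at 0.

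**2. Does Section 5 hold the input?**

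Items in 5.1 to 5.12: 1 + 2 + 5 + 3 + 3 + 6 + 2 + 5 + 6 + 2 + 2 + 1 = 38. Neutrophil count, lymphocyte count, blood count or NLR: 0.

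| Secondary clinical objective (4.2.2) | Items in Section 5 |
|---|---|
| PFS and OS | 5.6 start date, 5.7, 5.10, 5.11 |
| PFS rates at 6, 12, 18, 24 months | the same |
| Disease control rate | 5.8 |
| Duration of treatment | 5.6 |
| Time to response | 5.8, indirectly (cycles before first response; no date of first response) |
| Safety, including immune-related events | 5.9 (no separate immune-related flag) |
| NLR | none |

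Six of seven objectives have at least one item, and NLR has none. Outside the objective, the only neutrophil measure in the protocol is the ANC eligibility threshold in Appendix 3. That is an entry criterion of the EAP and not a collected variable.

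**The case against.** The strongest reply is that this is mostly a matter of wording. The objective is secondary, it says potential, and no test, cut-off or selection rule is attached to it. Section 2.3 itself calls MMR status predictive on the strength of a trial for which it describes no untreated group. The protocol may therefore simply use the word for any marker related to outcome under treatment. That is a fair reading of the usage, but it does not rescue the objective. Potential softens the expected result and leaves unchanged what can be estimated. If only an association is meant, the objective can say so.

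It is also true that whether an effect is modified depends on the endpoint and the scale, and the protocol names no endpoint for NLR. This limits how the illustration may be read, but a cohort without a comparator is uninformative about modification on every scale.

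On the data list, the separate eCRF specification may well contain blood counts, and Section 5 is brief elsewhere too, as the entries for time to response and immune-related events show. This stands. The finding is that the protocol's list does not match its objective, and missing data have not been shown. Nor does Section 8.4 claim to list every limitation, so its silence on the comparator is a minor point.

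Finally, the protocol does not say that NLR is to be measured before treatment. Pre-dose timing is the natural reading for a marker meant to predict the outcome of treatment, but it is a choice the sponsor should confirm.

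**Conclusion.** The objective is wrong as written. The design supports an association between NLR and outcome in dostarlimab-treated patients and nothing beyond it. This follows from the treated-only population and does not depend on the assumed rates in the illustration. Separately, NLR is the only one of seven secondary clinical objectives with no item among the 38 in Section 5. Whether the counts are collected anyway depends on the eCRF specification.

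The reach is limited to one secondary objective. It should be corrected because it determines what the study may claim about NLR. Certainty is high on the design point and on the mismatch in the text. How readers would take the label is a judgement.

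**What to change.** - In Sections 1.1.2 and 4.2.2, replace the objective with an exploration of the association of baseline NLR with outcome in dostarlimab-treated patients, and drop the word predictive. ORR, PFS and OS are suggested as outcomes, since the protocol names none. The cut-off and model can stay with the SAP.
- In Section 5.5, add the last absolute neutrophil count and the last absolute lymphocyte count before the first dose, with the sample date. Align the eCRF specification before extraction, or state in 5.5 that it already holds them.

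**Cost.** The claim becomes more modest. The data burden is three fields per patient: 3 × 100 = 300 to 3 × 110 = 330 entries at most, from existing charts. Section 12.1 requires ethics re-approval of the amendment. Because extraction takes place at a single visit in 50 to 60 sites, adding the fields beforehand is cheaper than reopening charts.

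**Feasibility.** The EAP was "available in Spain from January 2021 to September 2022". Pre-dose counts therefore meet the cut-off in Section 8.3 unless the first ethics approval, whose date is not given, came before a patient's count. The Appendix 3 threshold means a neutrophil count should be in the chart. No lymphocyte count is required there, so some may have to be entered as not available.

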4.2.3. Translational Objectives

- To compare centralized immunohistochemistry (IHC) re-testing with local testing.
- To compare centralized IHC re-testing results with two PCR-based techniques (Promega® and Idylla®) and with possible MMR gene alterations (genetic and epigenetic).
- To analyze the overall response rate and progression-free survival of the dMMR/MSI population selected by each biomarker technique: IHC, Polymerase chain reaction (PCR) Promega®, PCR Idylla®, or gene alteration (next generation sequencing (NGS)/hypermethylation).

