3. STUDY RATIONALE

There is a paucity of real-world data of patients with EC treated with dostarlimab, something that has an especial interest considering the limited evidence available with dostarlimab (only a phase I open-label study).

Moreover, there are only some discrete published studies comparing different dMMR/MSI-H approaches in EC and there are almost not data assessing their correlation to ORR of immunotherapy. To our knowledge only one phase II trial with avelumab made a comparison of dMMR/MSI-H tested by IHC, PCR or NGS, but only 15 patients were assessed in the dMMR cohort.

In January 2021, GlaxoSmithKline opened an EAP in Spain to make dostarlimab available to eligible women with recurrent or advanced dMMR/MSI-H endometrial cancer, a clear unmet medical need for these endometrial cancer patients.

EAPs allow patients with a serious or life-threatening disease or condition who are not otherwise eligible to participate in a clinical trial and have no other comparable or satisfactory therapeutic options to access drugs, with demonstrated benefit in clinical trials, that are pending approval.

This study seeks to evaluate the efficacy and tolerability of dostarlimab in recurrent or advanced dMMR/MSI-H endometrial cancer patients treated in a real world setting within the Spanish EAP. In addition, the translational study aims to assess the efficacy according to the biomarker technique used (IHC, PCR Promega®, PCR Idylla®, or gene alteration by NGS/hypermethylation).

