5.3. Endometrial Cancer History

- Initial diagnosis date
- Tumor histology (and degree of tumor differentiation for endometrioid subtype)
- Disease stage
- Recurrent or initial metastatic disease
- MMR (IHC / MSI-H / MMR genetic study/ MLH1 hypermethylation)

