APPENDIX 3. DOSTARLIMAB EAP INCLUSION/EXCLUSION CRITERIA

Inclusion Criteria

To be considered eligible to participate in this program, all of the following requirements must be met:

1. At least 18 years of age, able to understand the program procedures and agree to participate by providing written informed consent.
2. Histologically diagnosed endometrial cancer (note: all histologies are permitted except endometrial sarcoma [including carcinosarcoma]).
3. Patient has evidence of tumor DNA damage repair dysfunction (dMMR/MSI-H) via locally available, validated methodology.
4. Patient has progressed on or after platinum containing chemotherapy (and has received no more than 2 lines of anti-cancer therapy for recurrent or advanced (Stage \geq IIIB) disease (first or second line)); prior treatment with hormone therapies is acceptable and does not count towards the number of lines of therapy.
5. ECOG performance status of ≤ 2 .
6. Adequate organ and bone marrow function, as defined below:
 - a. Absolute neutrophil count (ANC) $\geq 1,500/\mu\text{L}$
 - b. Platelets $\geq 100,000/\mu\text{L}$
 - c. Hemoglobin ≥ 9 g/dL
 - d. Adequate liver and renal function:
 - Serum creatinine $\leq 1.5 \times$ upper limit of normal (ULN) or calculated creatinine clearance ≥ 50 mL/min using Cockcroft-Gault equation for patients with creatinine levels $> 1.5 \times$ institutional ULN.
 - Total bilirubin $\leq 1.5 \times$ ULN AND direct bilirubin $\leq 1 \times$ ULN.
 - Aspartate aminotransferase (AST) and alanine aminotransferase (ALT) $\leq 2.5 \times$ ULN unless liver metastases are present, in which case they must be $\leq 5 \times$ ULN.
7. Cannot be satisfactorily treated with available alternative treatments.
8. Not eligible for a clinical trial with dostarlimab within the indication of the EAP (where access to the clinical trial site is possible).

9. A female participant is eligible to participate if she is not pregnant or breastfeeding, and if one of the following conditions applies:

- Is a woman of non-childbearing potential (WONCBP)

OR

- Is a WOCBP and using a contraceptive method that is highly effective (with a failure rate of < 1 % per year), preferably with low user dependency, during treatment and for at least 4 months after treatment. The treating physician should evaluate the potential for contraceptive method failure (e.g., noncompliance, recently initiated) in relationship to the first dose of dostarlimab.

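### ORR and PFS reported only in patients positive by each technique come from overlapping subsets of one locally positive, treated cohort and answer the technique question weakly; central-versus-local testing can give little beyond a confirmation rate

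*Protocol*

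**What the plan says.** All from the protocol.

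- **Entry.** Section 4.5 states "Patients must meet all the following EAP inclusion criteria and none of the exclusion criteria to be eligible" and "Participants must have received dostarlimab (at least 1 cycle) within the Spanish EAP". The relevant criterion, number 3 in Appendix 3, is "Patient has evidence of tumor DNA damage repair dysfunction (dMMR/MSI-H) via locally available, validated methodology". The type of method is left open.
- **Local results.** Section 5.3 collects them by type: "MMR (IHC / MSI-H / MMR genetic study/ MLH1 hypermethylation".
- **Translational objectives** (sections 1.1.3 and 4.2.3). The first is "To compare centralized immunohistochemistry (IHC) re-testing with local testing". The second sets central IHC against two PCR kits and against MMR gene alterations. The third is "To analyze the overall response rate and progression-free survival of the dMMR/MSI population selected by each biomarker technique", the techniques being IHC, Promega PCR, Idylla PCR and gene alteration.
- **Purpose.** Section 3 notes that "there are almost not data assessing their correlation to ORR of immunotherapy" and says "the translational study aims to assess the efficacy according to the biomarker technique used".
- **Numbers.** Section 6 expects 100–110 patients with no formal sample size calculation. Section 9 restricts response to patients with measurable disease at the start of dostarlimab.
- **Limitations.** Section 8.4 covers chart review, missing data and under-recorded adverse events. It does not mention that every patient was selected on a positive local result.

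**The concern.** Whether a technique's result goes with response is a question about the difference between patients positive and patients negative by that technique. The third objective, as worded, reports outcomes only in the positives. Because all patients entered on a local positive result, the sets positive by IHC, Promega, Idylla and gene alteration share members, possibly most of them. ORRs that look alike could then reflect shared patients and say little about the techniques. The informative patients are those treated on a local positive result who are negative by a given central technique, and the objective does not mention them.

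The same selection affects the first objective. If overall local status is positive in everyone, central re-testing can confirm or fail to confirm, but there are no local negatives to agree on. Since the qualifying local method may differ from IHC, setting central IHC against local testing as a whole also mixes disagreement between laboratories with disagreement between methods.

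At stake is the translational report. A reader could take similar ORRs as showing that the techniques are interchangeable, when the analysis had little chance of showing otherwise.

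**Working it through.** The protocol gives no translational sample size, discordance rate or agreement figure, so there is no figure of its own to reproduce on this point.

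**Reference ORR.** Section 2.4.2 reports 45.5% among 143 evaluable patients (95% CI 37.1–54.0) in the earlier trial's dMMR endometrial cohort. That is 65/143, and the exact interval is 37.1–54.0%, as printed. It serves here only as an illustrative ORR.

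**Step 1: how far a positive-only ORR can move.** Let d be the share negative by a technique, and ORR+ and ORR− the response rates in its positives and negatives.

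ORR(all) = (1 − d) × ORR+ + d × ORR−, so ORR+ − ORR(all) = d × (ORR+ − ORR−).

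Take ORR+ = 45.5%. The values of d and ORR− are assumptions.

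| d | shift if ORR− = 0% | if 10% | if 20% |
|---|---|---|---|
| 2% | 0.9 points | 0.7 | 0.5 |
| 5% | 2.3 | 1.8 | 1.3 |
| 10% | 4.5 | 3.5 | 2.5 |
| 20% | 9.1 | 7.1 | 5.1 |
| 30% | 13.6 | 10.6 | 7.6 |

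**Step 2: precision of a single ORR.** 50/110 has exact 95% CI 35.9–55.2 (half-width 9.6 points). 46/100 has 36.0–56.3 (10.1). The measurable-disease restriction can only widen these. For d up to 10% the largest shift is under half of this half-width. At 20–30% it can equal or exceed it.

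**Step 3: the same data analysed two ways.** Assume 105 patients, 48 responders (45.7%, CI 36.0–55.7), and 10 negative by one technique.

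| Responses among the 10 negatives | Positive-only ORR (95% CI) | Positive v negative | Fisher p |
|---|---|---|---|
| 0 | 48/95 = 50.5% (40.1–60.9) | 48/95 v 0/10 | 0.002 |
| 2 | 46/95 = 48.4% (38.0–58.9) | 46/95 v 2/10 | 0.11 |
| 3 | 45/95 = 47.4% (37.0–57.9) | 45/95 v 3/10 | 0.34 |

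In every row the positive-only ORR is hard to tell from 45.7%. The contrast is clear only in the most favourable row. Varying the number of negatives with no responses among them gives 48/100 v 0/5, p = 0.06, and 48/90 v 0/15, p < 0.001.

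**Step 4: power of the contrast.** With N = 110, ORR+ = 45.5% and two-sided Fisher at 0.05:

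| Negatives | power if ORR− = 10% | if ORR− = 20% |
|---|---|---|
| 6 | 0.34 | 0.17 |
| 11 | 0.64 | 0.29 |
| 22 | 0.92 | 0.56 |
| 33 | 0.97 | 0.70 |

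**Step 5: central versus local.** With overall local status positive in all, the two-by-two table has one empty margin. Suppose central IHC confirms 99 of 110: 90.0% (exact CI 82.8–94.9). Observed agreement is 0.90, and chance agreement is 1 × 0.90 + 0 × 0.10 = 0.90. Kappa = (0.90 − 0.90)/(1 − 0.90) = 0, and it is 0 for any confirmation rate below 100%. Specificity and negative agreement have no denominator.

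**The case against.** **No discordance rate is given.** True, and this part of the objection stands. A reader might infer that the four sets are near-identical and their ORRs forced to be almost equal. The documents do not support that: the overlap is unknown. Section 11 defines the gene-alteration set by mutation or MLH1 hypermethylation and not by protein loss, so it could overlap much less with the IHC set.

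**The objective only says analyze.** It promises no ranking, test or equivalence claim, and section 9 leaves details to a SAP that is not at hand. Measures of agreement and the choice of analysis set are ordinary SAP content. But the objective itself fixes which patients the outcomes are reported in, and section 3 justifies the work by missing data on correlation with ORR. Positive-only subsets answer that weakly.

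**The data can address the question.** Also true. One might infer that the design cannot show any relation between technique and outcome. It can, because technique-negative patients were treated and have outcomes, and the second objective will identify discordant patients. The weakness is in the stated analysis. Even so, the contrast will be imprecise if negatives are few. With no untreated patients, it shows association with response among local positives and cannot establish treatment-specific benefit.

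**Local negatives may exist by method.** A patient who entered on local PCR could have had a local IHC showing no protein loss. The limit in step 5 therefore applies to overall local status, and a like-for-like IHC comparison might contain a few local-IHC negatives.

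**Conclusion.** The concern holds in a limited form. Selection on a local positive result makes the technique-selected populations overlapping subsets of one treated cohort, and reporting outcomes only in the positives is a weak way to assess efficacy by technique. If 10% or fewer are negative by a technique, its ORR can sit at most about 4.5 points from the whole-cohort ORR, within a half-width of about 10 points. At 20–30% negative the gap could be 9–14 points. These figures assume ORR+ = 45.5% and no responses among negatives, that response can be assessed in all 100–110 patients, and that each has a valid result on the technique. Similar ORRs would not demonstrate equivalence. Against overall local status, central re-testing yields a confirmation rate only. Section 8.4 is silent on this selection.

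This affects an exploratory part of the study, not the primary ORR and DOR objective.

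**What to change.** 1. **Sections 1.1.3 and 4.2.3, third objective.** For each technique, report ORR (difference with 95% CI) and PFS in technique-positive versus technique-negative treated patients. Use the common set with valid results on all techniques, with measurable disease for ORR, and list the discordant patients individually. Label the analysis descriptive, and say that it shows association with outcome among locally positive patients and not treatment-specific prediction.
2. **First objective.** State it as the share of local positives confirmed by central IHC, with exact 95% CI, separately for patients with local IHC and for those who entered on another local method. Note that against overall local status specificity and negative agreement are not estimable and kappa is uninformative.
3. **Section 8.4.** Add selection on local positivity as a limitation.

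The cost is wording in the protocol and the matching analysis plan. The assays are already planned in section 11, and local method and outcomes are already collected under section 5. The downside is that technique-negative groups may be small and their intervals wide, and that requiring valid results on all techniques may reduce the number analysed.
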